### **9.3.3 Efficacy Analysis for Secondary Endpoints**

The secondary efficacy endpoints include changes from baseline at the end of double-blind period (at Week 24) of 2h PPG, and FPG. The same analysis method for the primary efficacy endpoint is used, i.e. MMRM. The adjusted least-squares mean difference between HMS5552 and placebo, and its 95% CI is estimated by MMRM.

HbA1c response rate is calculated based on the data imputed by last observation carried forward (LOCF). The HbA1c response rate, i.e. number and percentage of subjects whose HbA1c is less than 7.0% at the end of double-blind treatment period (at Week 24) are summarized. The HbA1c response rate and 95% CI for each group are estimated using the logistic regression method.

The measurement and changes of HbA1c, FPG and 2h PPG from the end of double-blind period (Week 24) to the end of study (Week 52) are summarized by two groups: one group is for subjects who are randomized into HMS5552 treatment group, and the other group is for subjects who are randomized into placebo group while switched to HMS5552 open-label treatment after double-blind period (Week 24). The measurements at the end of double-blind period (Week 24) are used as baseline for the summary of the measurements and change from baseline at each visit in the open-label period.

### **9.3.4 Safety Analysis**

Descriptive analysis is performed on SS. Safety data are summarized and evaluated for the following two stages: 1) Stage 1: when the subjects completed the double-blind period, and 2) Stage 2: when the whole study is completed.

All AEs are coded using the MedDRA dictionary. The incidences and severity of AEs, and SAEs etc. are summarized and compared between two treatment groups. The detailed description of the treatment emergent SAE and study discontinuation due to AE is listed.

The incidence of hypoglycemic events is compared between treatment groups. The incidence ratio and 95% CI of each treatment group, as well as the incidence difference between treatment groups and its 95% CI are calculated.

The change from baseline of laboratory tests, physical examinations, vital signs, and 12-lead ECG measurements at each visit are summarized. Each index before and after treatment of normal/abnormal changes is also summarized.

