## 7.10 12-lead ECG

A 12-lead ECG examination is conducted at each visit except Visit 2 and Visit 16. The Investigator evaluates the ECG results and records the results on eCRF as “normal” or

“abnormal with/without clinical significance”. See Section 7.1.3 AEs Related to Examinations and Laboratory Tests for how to record and report AEs related to laboratory examinations.

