### Pulse rate

Palpation on the radial artery is suggested to last for at least 30 seconds to calculate the number of beats per minute, which is recorded on eCRF. If necessary, palpation is on bilateral radial artery simultaneously to check the symmetry. It is recommended to be marked on eCRF if there is any asymmetry.

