### **9.3.6. 12-lead ECG**

Normality / abnormality of test results from baseline to post-treatment will be described. Subjects who are normal at baseline while abnormal with clinical significance after treatment or who are abnormal without clinical significance at baseline while abnormal with clinical significance after treatment will be listed.

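### The protocol plans change from baseline in 12-lead ECG measurements by visit, but the ECG record and SAP described give only a three-level judgement, so mean shifts in ECG intervals cannot be estimated

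*Supplement*

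**What the plan says.** Protocol v1.1 lists the 12-lead ECG as a safety endpoint (3.1.3). On timing, section 7.10 says: "A 12-lead ECG examination is conducted at each visit except Visit 2 and Visit 16". That is 14 of the 16 visits.

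Three places then describe what is done with the tracings:

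- **Protocol 9.3.4 (planned analysis).** "The change from baseline of laboratory tests, physical examinations, vital signs, and 12-lead ECG measurements at each visit are summarized". The next sentence adds a second summary: "Each index before and after treatment of normal/abnormal changes is also summarized".
- **Protocol 7.10 (what is recorded).** The "Investigator evaluates the ECG results and records the results on eCRF as" normal or "abnormal with/without clinical significance". This gives three levels.
- **SAP 9.3.6 (final analysis).** "Normality / abnormality of test results from baseline to post-treatment will be described". It also lists subjects who move to a clinically significant abnormality, either from normal or from abnormal without clinical significance.

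Protocol 9.3 requires the SAP to record departures from the protocol's planned analysis. The table of changes in SAP 2.1 has no ECG entry.

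**The concern.** A change from baseline in a measurement needs a measured value at both times. A three-level judgement supplies none, so the first of the two summaries in 9.3.4 cannot be produced from the record that 7.10 describes, and the SAP does not attempt it.

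At stake is the trial's ability to describe small systematic effects of the drug on cardiac conduction and repolarisation. A modest average lengthening of PR, QRS or QT that leaves most tracings in the same category would not show in a shift table. This applies also to subjects whose ECG is already graded abnormal at entry. The eligibility criteria allow such subjects when the investigator does not think the abnormality affects the safety evaluation or needs intervention, and they make an exception for stable coronary heart disease. In these subjects an interval can lengthen without the grade changing.

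**Working it through.** The point turns on data capture against planned analysis, and the plan gives no ECG figure to reproduce. The main check is therefore a comparison of the texts.

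**Step 1: are two ECG summaries intended?** Yes, on the natural reading. Protocol 9.3.4 gives change from baseline by visit in one sentence, and in the next says that normal/abnormal changes are also summarised. The second would add nothing if the first were only the category shift.

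**Step 2: what values are named?** No section of protocol v1.1 or the SAP names PR, QRS, QT or QTc, an ECG heart rate, or a central reading. Section 7.10 names only the three-level judgement.

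**Step 3: how does the SAP treat the items listed beside the ECG?**

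| Item | SAP section | Numeric change or descriptive statistics | By visit |
|---|---|---|---|
| Vital signs | 9.3.5 | Yes, change from baseline | Yes |
| Laboratory tests | 9.3.7 | Yes, mean, SD and quartiles for continuous parameters | Stated for categorical parameters |
| 12-lead ECG | 9.3.6 | No | No (baseline to post-treatment) |

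**Step 4: is any of the loss made good elsewhere?** For heart rate, yes. Under Vital Signs (7.11) the pulse is palpated to "calculate the number of beats per minute, which is recorded on eCRF". It is taken at the same clinic visits from Visit 4 to Visit 15, and SAP 9.3.5 summarises its change from baseline. For the intervals, no other source is described.

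**Step 5: illustration of the information lost.** Every QTc input here is an assumption, because the documents give none: mean 415 ms; SD of a single value and of the change both 20 ms; abnormal taken as above 450 ms; two-sided 5% level. The arm sizes of 300 and 150 are the planned 450 subjects at 2:1.

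- Numeric values: SE of the arm difference in mean change = 20 × √(1/300 + 1/150) = 20 × 0.1 = 2.0 ms.
  - 10 ms shift: power = Φ(10/2.0 − 1.96) = Φ(3.04) = 99.9%.
  - 5 ms shift: power = Φ(5/2.0 − 1.96) = Φ(0.54) = 71%.
- Categories: the control proportion above 450 ms is 1 − Φ(35/20) = 4.0%.
  - 10 ms shift: the drug-arm proportion is 1 − Φ(25/20) = 10.6%.
  - 5 ms shift: the drug-arm proportion is 1 − Φ(30/20) = 6.7%.
  - Power of Fisher's exact test, by summing over all binomial outcomes with 300 and 150 subjects: about 68% for 10 ms and 17% for 5 ms.

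Varying the assumed SD, with the mean and cut-off unchanged:

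| SD (ms) | SE (ms) | 10 ms: numeric / category | 5 ms: numeric / category |
|---|---|---|---|
| 15 | 1.5 | >99.9% / 55% | 92% / 7% |
| 20 | 2.0 | 99.9% / 68% | 71% / 17% |
| 25 | 2.5 | 98% / 64% | 52% / 18% |

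These figures compare the information in two forms of the same data at one visit. They do not give the power of any analysis in the plan.

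**The case against.** The strongest reply is that this is a wording mismatch with a modest consequence. Its parts fare differently.

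- **Heart rate is covered.** A reader might infer that the trial could miss a drug effect on heart rate. The documents do not support that, because pulse rate is recorded as a number and its change is summarised by visit. This part of the reply stands in full.
- **Important changes would still be seen.** A reader might infer that the ECG endpoint cannot detect a drug effect at all. That is too strong. SAP 9.3.6 lists worsening to clinical significance, including from an already abnormal baseline, and protocol 7.1.3 makes an abnormality that points to new or worsened disease or organ toxicity a reportable adverse event. What is lost is sensitivity to mean and sub-threshold shifts.
- **Section 7.10 does not say that nothing else is entered.** The SAP cites a CRF and refers to table shells that are not shown, and SAP 7.2 summarises baseline ECG without naming variables. The absence of numeric fields is therefore an inference. If the fields exist, the SAP still omits an analysis that the protocol plans.
- **The sentence in 9.3.4 is generic.** It also promises change from baseline for physical examinations, which are not numeric. This weakens a purely literal reading, but does not explain why the ECG has no by-visit summary or why SAP 2.1 is silent.
- **The protocol sets no explicit interval question.** This is correct, and any earlier ECG data lie in an Investigator's Brochure that is not available here.
- **The stakes are smaller than 14 visits suggests.** Three of those ECG visits (1, 3 and 4) are at or before baseline, and after Visit 10 every subject receives HMS5552. Only Visits 5 to 10 give placebo-controlled post-baseline ECGs. This stands.

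**Conclusion.** The point holds in a limited form. Protocol 9.3.4 plans a by-visit change from baseline in ECG measurements. Neither the record described in 7.10 nor SAP 9.3.6 can deliver it, and the reduction is not documented in SAP 2.1 as protocol 9.3 requires. On the data described, mean or sub-threshold shifts in PR, QRS and QT/QTc cannot be estimated. Heart rate, and ECG changes judged clinically significant, remain visible.

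The conclusion rests on one inference, that the CRF has no numeric ECG fields. If it has them, the fault moves from data capture to the SAP. The power figures show only how much information grading can lose under assumed QTc values. Safety analysis is descriptive, no test of ECG status is specified, and the illustration reduces three levels to two. The primary efficacy analysis is unaffected. This is a worthwhile, inexpensive improvement to a safety summary.

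**What to change.** 1. Record PR, QRS and QT from each ECG already performed, with the heart rate from the same tracing so that QTc can be derived by one stated formula. This assumes that the printouts give these values, which the documents do not say.
2. Add to SAP 9.3.6 the mean change from baseline by visit and arm, with the between-arm difference and its 95% CI for the double-blind visits, and counts by pre-stated categories of QTc value and QTc increase. Keep the existing shift table and listing.
3. If the CRF already holds the values, only step 2 is needed.
4. If the values cannot be obtained, align protocol 9.3.4 with 7.10 and SAP 9.3.6 and enter the reduction in SAP 2.1. That mends the inconsistency but gives up the planned summary.

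The cost is a few eCRF fields, transcription time at the sites and two tables. No new procedure or visit is needed.

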### **9.3.5 Biomarker Analysis**

This section is not applicable.

### **9.3.6 Sensitivity Analysis**

Sensitivity analysis is applicable to the primary efficacy endpoint.

The LOCF approach is performed to impute missing primary efficacy endpoint. For subjects with early withdrawal, the last available post-treatment measurement is carried forward. The analysis of covariance (ANCOVA) model is used for analyzing the imputed data. The ANCOVA model includes baseline HbA1c value, disease duration, sites and groups as covariate, with or without the interactions between center and group. The adjusted least-squares mean difference between HMS5553 and placebo, and its 95% CI are estimated by ANCOVA. If p value of the between-group comparison is smaller than 0.05, it is considered that the between-group difference is statistically significant. If the upper limit of the 95% CI is smaller than 0, it is considered that HMS5552 is superior to placebo in treatment effect.

### **9.3.7 Interim Analysis**

No interim analysis is planned during the double-blind period. Statistical analysis is planned for two stages: 1) Stage 1 is for double-blind period, and 2) Stage 2 is for open-label period. After the completion of the double-blind period, the eligible subjects will enter the open-label period. No alpha sparing or independent data monitoring committee is required in this study.

## **10. Population PK/PD (PopPK/PD) Analysis**

The PopPK/PD model for HMS5552 in subjects with T2DM is updated by using the NONMEM/PIRANA/R software based on the current HMS5552 PopPK/PD model and PK/PD data in Chinese subjects with T2DM after HMS5552 treatment. The quantitative relationship between HMS5552 concentration and HbA1c level is established. Systemic quantitative analysis is conducted on the influences of various factors on HMS5552 PK/PD characteristics, e.g., demographic characteristics, disease course, and concomitant medications. The specific methods and information for analysis of PopPK/PD model are elaborated in the population

PK/PD analysis plan.

## **11. Study Management**

### **11.1 Declaration**

This study is conducted in full compliance with the Declaration of Helsinki, China Good Clinical Practice (GCP), China clinical study laws and regulations.

### **11.2 Ethics Committee**

In accordance with China regulatory requirements, all study related documents are provided to ethics committee (EC) by the Investigator.

Before the study drugs are shipped to the Investigator, the copy of EC approval and the list of required documents must be provided to the Sponsor. The documents approved by EC should include a list of EC members who have taken part in the discussion for document approval.

Upon receipt of the EC approval, the Sponsor/CRO should submit the study related documents to the relevant drug evaluation authority for record.

Approval of the study from EC and drug administration department must be obtained before the study starts.

Protocol amendments need to be submitted to EC for approval. The health bureau is also notified per local requirements.

During the study, the Investigator should notify EC of any SAEs or unexpected AEs that are related to the safety of clinical study and may affect patient safety and study implementation.

The possible benefits and risks for subjects are fully described in the ICF.

### **11.3 Source Document Verification**

The Investigator must handle all data obtained from clinical study properly to protect the rights and privacy for the subjects participating in the study. The Investigator and the medical institution which he/she works in allow the Sponsor to monitor or audit the study. Health administration and drug administration departments have the right to inspect the study and review data/source documents.

### **11.4 Quality Control and Quality Assurance**

This study is audited for quality assurance by the Sponsor or Sponsor authorized personnel independent of the study, or be inspected and audited by drug evaluation authority. The quality assurance auditor or inspector from drug evaluation authority can review all study related information and documents, including but not limited to medical records, study documents and correspondence, study facilities and equipment, study samples and materials, etc.

The audit on the study by the Sponsor is part of quality assurance procedures. The audit conducted by the sponsor is different from the routine clinical study monitoring, and is also different from the routine quality control work in the functional department of the Sponsor. The objectives for the audit conducted by the Sponsor are: to evaluate the study implementation, and to evaluate the compliance with the study protocol, SOPs, related laws and regulations from the drug administration authorities.

### **11.5 Subject Informed Consent**

The Investigator is responsible for explaining to each subject about the study objectives, study methods, benefits, and potential risks. ICF signed by subjects must be obtained before any study related procedures. The informed consent should be presented both orally and in writing. The ICF also must be dated and signed by subjects. For subjects who cannot sign by themselves for any reason, the ICF must be signed by their parents, legal guardians or legal representatives. The signed ICF is kept by the subjects.

By signing the ICF, subjects/patients must agree to allow the Sponsor, regulatory authorities, auditors and/or monitors to verify the related original data obtained from the study. All the auditing personnel must follow the confidentiality agreement.

### **11.6 Protocol Amendment**

After the protocol is finalized, any protocol amendments must be documented in details and the records for protocol changes need to be signed at least by the Investigator and the Sponsor. The version numbers and dates need to be indicated.

All protocol amendments must be submitted to EC. Written approval must be obtained from EC for significant changes. Local regulatory authorities should also be notified with renewed profiles. All documents should be submitted to the Sponsor. All the procedures should be completed before the updated profile takes effect. Before the amended protocol takes effect officially, the previous protocol should be followed.

### **11.7 Monitoring**

On-site monitoring is performed by the CRAs from the Sponsor or Sponsor authorized CROs (the CROs' SOPs, the Sponsor's SOPs, or a written agreement between the parties should be followed). The monitoring visits should be conducted regularly throughout the study.

Monitors authorized by the Sponsor are permitted to review the source data relevant to the study and will verify the data on eCRFs and in other study documents per SOP and GCP requirements, ensuring data integrity, accuracy and consistency with the source documents.

All source documents, data, records, laboratory data/information, eCRF and medical test results must be accessible to monitors, inspectors and the drug administration departments for review at any time.

## **11.8 Confidentiality Agreement and Patient Privacy**

The Investigator must keep the information related to the Sponsor and investigational drug confidential, which is provided or disclosed due to the cooperation in the study. The information can only be used with authorization from the Sponsor.

The commitment to confidentiality is independent, valid, and persistent.

The Investigator should ensure that the confidential information is not disclosed to third parties and is only used within the agreed scope. The confidential information may be obtained from Hua Medicine and its products, or provided or disclosed due to the contractual relationship.

The clinical study staffs must protect subjects' privacy. Only the subject number can be used for subject's identification in all documents submitted to the Sponsor. Subjects' names and hospitalization IDs cannot be used. The Investigator must properly preserve the relevant documents related to subjects' names, addresses and the screening IDs/randomization IDs. All subjects' information should be securely preserved by the Investigator in accordance with GCP regulations.

## **12. Publication**

As the Sponsor, Hua Medicine (Shanghai) Ltd. has the exclusive ownership for the publications in this study. Authors and publications reflect the collaboration among multiple investigators, study sites and staffs from Hua Medicine (Shanghai) Ltd.. Authors should be determined before preparing the manuscript. Unless approved by Hua Medicine (Shanghai) Ltd., any person is not allowed to have any publication before the final clinical study report is completed. Hua Medicine (Shanghai) Ltd. has the right to make final decision on all manuscripts and publications.

## **13. Documents Archiving**

In accordance with relevant regulations, the Investigator should maintain all the medical source documents properly. All study documents should be kept for at least 5 years after the drug is marketed. The Sponsor is responsible for informing the Investigator/study sites when the study documents do not need to be kept any more.

## 14. Appendix

### Appendix 1 Diagnosis of Diabetes Mellitus

(From China Guideline for Type II Diabetes prevention and treatment, Version 2013, CDS)

Clinical diagnosis for diabetes mellitus should be based on the blood test results of venous plasma glucose rather than capillary blood glucose. If not specified, the blood glucose mentioned in this article refers to the venous plasma glucose.

The normal range of blood glucose and the diagnosis cutoff point for glucose metabolism abnormality are mainly confirmed by the relationship between the value of blood glucose and the risk of specific chronic diabetic complications (diabetic retinopathy) and diabetes mellitus occurrence. Currently, the commonly used diagnostic criteria and classification are the WHO standards (1999) and the ADA (American Diabetes Association) standards (2003).

This guideline adopts WHO Standards (1999) for diabetes diagnosis, classification of glucose metabolism state, and the classification system of diabetes mellitus (Table 1 and 2). Fasting Plasma Glucose (FPG) or the venous plasma glucose value 2 hours after 75g Oral Glucose Tolerance Test (OGTT) alone can be used for epidemiological investigation or population screening. However, based on the data in our country, the missed diagnosis rate is high if only FPG is tested. Ideally, both FPG and venous plasma glucose 2 hours after OGTT need to be tested. Blood glucose at other time points after OGTT are not used as diagnostic criteria.

The population with impaired glucose regulation is suggested to take the OGTT to reduce the missed diagnosis rate.

**Table 1 Classification of Glucose Metabolism State (WHO 1999)**

Classification of Glucose Metabolism	Venous Plasma Glucose (mmol/L)	
	Fasting Plasma Glucose	2 hours Postload Plasma Glucose
Normal Plasma Glucose	< 6.1	< 7.8
Impaired Fasting Glucose (IFG)	6.1 ~ < 7.0	< 7.8
Impaired Glucose Tolerance (IGT)	< 7.0	7.8 ~ < 11.1
Diabetes Mellitus	≥ 7.0	≥ 11.1

Note: both IFG and IGT are called as impaired glucose regulation, also known as prediabetic state.

**Table 2 Diagnostic Criteria for Diabetes Mellitus**

Diagnostic Criteria	Venous Plasma Glucose (mmol/L)
---------------------	--------------------------------

---

(1) Typical diabetic symptoms (polydipsia, polyuria, polyphagia, and weight loss), with random plasma glucose test  $\geq 11.1$

Or, *with*

(2) Fasting plasma glucose test  $\geq 7.0$

Or, *with*

(3) Blood glucose test 2 hours postload glucose  $\geq 11.1$

People without diabetic symptoms needs re-test on different day

---

Note: The fasting status means no calories intake for at least 8 hours; random plasma glucose means plasma glucose tested at any time regardless of the last meal time and can't be used for IFG and IGT diagnosis.

